3.8.2.2 Injection Site Reactions

Analysis of ISRs will include summaries of the following assessments (defined in Section 3.3.1.1)

- Pain, tenderness, erythema, and induration severity, and lymphadenopathy (categorical variables with grades 1-4, and absent).
- Erythema and induration: record the maximum linear diameter
- Blisters, ulceration, necrosis: record the maximum linear diameter and severity
 For both of these assessments, the maximum linear diameter will be summarized.

3.8.3 Clinical Laboratory Evaluation

A list of the clinical chemistry, hematology, and coagulation analytes are listed in Table 1. The exception being PNH clone size which will be summarized in a separate table but included in the hematology listing.

Quantitative laboratory endpoints will be summarized by time point using descriptive statistics.

Urinalysis parameters which do lend themselves to analyses (i.e., "Color") will be presented in the listings only.

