9.2 EXCLUSION CRITERIA

Subjects who meet **ANY** of the following exclusion criteria must be excluded from the study:

1. Platelet count <30,000/ μ L or absolute neutrophil count (ANC) <500 cells/ μ L at Screening
2. Calculated glomerular filtration rate of <30 mL/min/1.73m² based on modification of diet in renal disease (MDRD) equation at Screening
3. Elevation of liver function tests: alanine aminotransferase (ALT) >2xULN or Direct Bilirubin and Alkaline Phosphatase (ALP) both >2xULN
4. Elevation of amylase or lipase >2xULN
5. History of meningococcal disease
6. Current systemic infection or suspicion of active bacterial infection
7. Pregnant, planning to become pregnant, or nursing female subjects
8. Recent surgery requiring general anesthesia within the 2 weeks prior to Screening, or expected to have surgery requiring general anesthesia during the 12-week Treatment Period
9. Active malignancy requiring surgery, chemotherapy, or radiation within the prior 12-months (subjects with a history of malignancy who have undergone curative resection or otherwise not requiring treatment for at least 12-months prior to Screening with no detectable recurrence are allowed)
10. History of any significant medical or psychiatric disorder that in the opinion of the investigator would make the subject unsuitable for participation in the study
11. Treatment with any investigational medicinal product or investigational device within the 30 days prior to Screening or participation in another concurrent clinical trial involving a therapeutic intervention (participation in observational studies and/or registry studies is permitted)
12. Unable or unwilling to comply with the requirements of the study

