12.1.3.2 HEPATIC ADVERSE EVENTS

All subjects should be monitored for signs and symptoms of hepatic or biliary dysfunction. Liver function tests (LFTs) (ALP, ALT, AST, GGT, Direct Bilirubin and Indirect Bilirubin) are monitored weekly for the first 4 weeks followed by every 2 weeks during the study. The following guideline is provided:

- In subjects with isolated ALT elevation $>2xULN$ or direct bilirubin and ALP elevation $>2xULN$ with no other explanation for the elevation(s), contact the medical monitor to review the case details and determine if the subject should continue or discontinue study treatment. The subject should be monitored until the elevated enzymes return to Grade 1 (NCI CTACE) or lower.
- Subjects with isolated ALT elevations $>3xULN$ concurrently with bilirubin elevation $\geq 2xULN$ and a normal ALP with no other explanation for the elevation should be permanently discontinued. The medical monitor should be contacted as soon as possible to review the case. The subject should be monitored until the elevated enzymes return to Grade 1 (NCI CTACE) or lower.

All AEs should be recorded as AEs per Section 12.1 and 12.3.

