13.3.4.2.2 HEPATIC ADVERSE EVENTS

Hepatic and biliary AEs and will be summarized separately by system organ class, preferred term, and cohort. Liver function tests will be summarized by changes from baseline and graded in severity using the NCI CTCAE criteria.

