13.3.4.2.3 PANCREATIC ENZYME ELEVATIONS

Pancreatic AEs and will be summarized separately by system organ class, preferred term, and cohort. Pancreatic elevations will be summarized by changes from baseline and graded in severity using the NCI CTCAE criteria.

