3.8.3.1 Hepatic Laboratory Tests: NCI CTCAE Grading

The liver functions test to be summarized via the National Cancer Institute (NCI) Common Terminology Criteria for Adverse Events (CTCAE) criteria are provided in Table 7.

Table 7: CTCAE Grading Criteria for Selected Liver Function Tests

	Grade/Criteria				
1	2	3	4		
> 1.0 - 3.0	>3.0 - 5.0	>5.0 - 20.0	> 20.0		
(x ULN)	(x ULN)	(x ULN)	(x ULN)		
>1.0 - 2.5	>2.5 - 5.0	>5.0 - 20.0	> 20.0		
(x ULN)	(x ULN)	(x ULN)	(x ULN)		
> 1.0 – 1.5	>1.5 – 3.0	>3.0 - 10.0	> 10.0		
(x ULN)	(x ULN)	(x ULN)	(x ULN)		
>1.0 - 2.5	>2.5 - 5.0	>5.0 - 20.0	>20.0		
(x ULN)	(x ULN)	(x ULN)	(x ULN)		
,	,	,	,		
	(x ULN) >1.0 - 2.5 (x ULN) > 1.0 - 1.5 (x ULN) >1.0 - 2.5 (x ULN)	(x ULN) (x ULN) >1.0 - 2.5 >2.5 - 5.0 (x ULN) (x ULN) > 1.0 - 1.5 >1.5 - 3.0 (x ULN) (x ULN) >1.0 - 2.5 >2.5 - 5.0 (x ULN) (x ULN)	(x ULN) (x ULN) (x ULN) >1.0 - 2.5 >2.5 - 5.0 >5.0 - 20.0 (x ULN) (x ULN) (x ULN) > 1.0 - 1.5 >1.5 - 3.0 >3.0 - 10.0 (x ULN) (x ULN) (x ULN) >1.0 - 2.5 >2.5 - 5.0 >5.0 - 20.0		

Grading criteria based on Common Terminology Criteria for Adverse Events (CTCAE) v4.03

Note: CTCAE ULN grades for direct bilirubin based on CTCAE ULN grades for total ("blood") bilirubin

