3.8.3.2 Pancreatic Enzymes: NCI CTCAE Grading

Amylase and lipase values will be summarized via the NCI CTCAE criteria provided in Table 8.

Table 8: CTCAE Grading Criteria for Selected Pancreatic Enzyme Tests

Lab Test	Grade/Criteria					Grade/Criteria			
	1	2	3	4					
amylase	> 1.0 – 1.5	>1.5 – 2.0	>2.0 - 5.0	> 5.0					
	(x ULN)	(x ULN)	(x ULN)	(x ULN)					
limana	> 1.0 – 1.5	>1.5 – 2.0	>2.0 - 5.0	> 5.0					
lipase	(x ULN)	(x ULN)	(x ULN)	(x ULN)					
Grading criteria based on Common Terminology Criteria for Adverse Events (CTCAE) v4.03									

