3.8.6 Vital Signs and Other Physical Findings

Descriptive statistics for vital signs (i.e. heart rate, body temperature, and blood pressure) values and the change from baseline will be presented.

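### The SAP omits the change-from-baseline summaries that the protocol commits to for liver tests and pancreatic enzymes, and does not link its CTCAE grade tables to baseline

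*SAP*

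**What the plan says.** For the hepatic events of special interest, Protocol 13.3.4.2.2 states: "Liver function tests will be summarized by changes from baseline and graded in severity using the NCI CTCAE criteria". For the pancreatic ones, Protocol 13.3.4.2.3 states: "Pancreatic elevations will be summarized by changes from baseline and graded in severity using the NCI CTCAE criteria". Each sentence promises two things, a change and a grade.

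SAP 3.8.3 covers laboratory data in general: "Quantitative laboratory endpoints will be summarized by time point using descriptive statistics". Two subsections add grading. SAP 3.8.3.1 names the "liver functions test to be summarized via the National Cancer Institute (NCI) Common Terminology Criteria" and gives Table 7. SAP 3.8.3.2 says "Amylase and lipase values will be summarized via the NCI CTCAE criteria provided in Table 8". Neither subsection mentions change from baseline, a baseline grade, or whether grades are counted by visit or as the worst value after dosing.

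By contrast, SAP 3.8.6 says of vital signs that "values and the change from baseline will be presented", and SAP 3.8.7 does the same for ECG parameters.

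**The concern.** The protocol treats hepatic events and pancreatic enzyme elevations as adverse events of special interest (12.1.3.2 and 12.1.3.3). With no control arm, a subject's own pre-dose value is the only reference for judging a laboratory change. The SAP follows that principle for adverse events but does not carry it into the laboratory grading.

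The gap matters more because the separate hepatic and pancreatic adverse event summaries promised in the same two protocol sections are also missing from SAP 3.8.2 and the table list. That leaves the laboratory grade tables as the only dedicated summaries of these two risks. If they do not link a subject's grades before and after dosing, the study report cannot show from its tables who worsened.

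**Working it through.** The plan states no figure on this point. The check compares the sections and then maps the entry limits onto the grade bands.

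**1. Promise against specification**

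| Item | Protocol | SAP |
|---|---|---|
| Liver tests: CTCAE grade | 13.3.4.2.2, yes | 3.8.3.1, yes |
| Liver tests: change from baseline | 13.3.4.2.2, yes | not stated |
| Amylase, lipase: CTCAE grade | 13.3.4.2.3, yes | 3.8.3.2, yes |
| Amylase, lipase: change from baseline | 13.3.4.2.3, yes | not stated |

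Protocol 12.1.3.2 lists the liver tests as "ALP, ALT, AST, GGT, Direct Bilirubin and Indirect Bilirubin) are monitored weekly". No SAP section applies change from baseline to any of these six, or to amylase or lipase. Total bilirubin does keep it, as a secondary efficacy endpoint (SAP 3.9.2), but it is not on that list.

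**2. Is the summary implied elsewhere?** SAP 3.1.3 defines change from baseline. Individual sections then say where it applies: 3.8.6, 3.8.7, 3.9.1, 3.9.2, 3.9.3 and 3.9.5.1 to 3.9.5.3. The laboratory section is not among them. Shift tables are specified for FACIT-Fatigue items and EQ-5D dimensions, in the text and in the table titles. Tables 14.3.2.5 and 14.3.2.6 are titled as values and grading only. Other reductions are announced (anti-drug antibodies in 3.8.4, CH50 in 3.9.3); this one is not.

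**3. Grades a subject can have at entry.** Exclusion criterion 4 in Protocol 9.2 reads "Elevation of amylase or lipase >2xULN", so values up to 2.0 x ULN are admitted. Criterion 3 excludes ALT above 2 x ULN, and excludes direct bilirubin and ALP only when both exceed 2 x ULN.

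| Analyte | Admitted at entry | SAP grade |
|---|---|---|
| Amylase, lipase | >1.0 to 1.5 x ULN | 1 |
| Amylase, lipase | >1.5 to 2.0 x ULN | 2 |
| ALT | >1.0 to 2.0 x ULN | 1 (row assumed) |
| Direct bilirubin | >1.5 to 3.0 x ULN; above 2.0 only if ALP is not above 2 x ULN | 2 (row assumed) |
| Direct bilirubin | >3.0 x ULN, if ALP is not above 2 x ULN | 3 or higher (row assumed) |
| ALP | no ceiling if direct bilirubin is not above 2 x ULN | no upper bound on grade, if graded |
| AST, GGT | no limit | no upper bound on grade, if graded |

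The row labels of SAP Table 7 are not legible in the text available. I assume that the row starting at >1.0-3.0 is ALT/AST and the row starting at >1.0-1.5 is direct bilirubin; the table note supports the latter. The amylase and lipase rows of Table 8 are fully legible and need no assumption.

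**4. Weight of one subject.** 1/12 = 8.3%, 1/8 = 12.5%, 1/6 = 16.7%. The documents give no expected number of subjects entering with a grade, so this only illustrates scale.

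**5. What counts by visit can and cannot show.** Suppose one subject enters at Grade 2 lipase and stays there. A table with a baseline column shows 1/n at Grade 2 before dosing and at every visit, and no rise appears. Now suppose one subject moves from Grade 0 to Grade 2 while another moves from Grade 2 to Grade 0. The counts are again one at Grade 0 and one at Grade 2, before and after, so the worsening is invisible without linking each subject's grades. If the table reports worst post-baseline grade with no baseline column, the unchanged subject cannot be told from a new Grade 2.

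**The case against.** A reader might infer that pre-existing abnormalities will be reported as on-treatment toxicity. The documents do not support that. Nothing in SAP 3.8.3 to 3.8.3.2 confines the tables to post-baseline values, and chemistry is drawn at Screening and Day 1, so summaries by time point can include the pre-dose value. SAP 3.8.1 counts an event already present at treatment start as treatment-emergent only if it becomes more severe, so a stable elevation does not qualify. A reader might also infer that a baseline column would be no help; step 5 shows that it does reveal the unchanged subject.

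Other points on that side carry weight. All data are listed by patient (SAP 3.1.2, Listing 16.2.12.2), and with at most 20 subjects the courses can be read individually. The table shells are a separate document and were not available. Table titles alone prove little: those for ECG and vital signs do not mention change, yet the text requires it. The SAP also says that it builds on protocol Section 13.

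Finally, the protocol promises changes and grades, not shift tables, and a rule counting only rises of a full grade would have its own blind spot. On the assumed ALT row, a rise from 1.1 to 2.9 x ULN stays within Grade 1, although it crosses the 2 x ULN level at which Protocol 12.1.3.2 calls for contact with the medical monitor.

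These points limit the consequence but do not remove the omission. Listings are not the promised summary, and shells cannot stand in for a rule that the SAP text does not contain.

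**Conclusion.** The SAP leaves out, without explanation, a safety summary that the protocol commits to, and it specifies no baseline-linked summary of grades. For amylase and lipase, the entry criteria admit subjects already at Grade 2 under the SAP's own bands. For isolated direct bilirubin, isolated ALP, AST and GGT there is no entry ceiling. The summary tables as specified therefore could not separate pre-existing from treatment-emergent grades within subjects; listings and any baseline column would show this in part.

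The size cannot be stated beyond the illustrative 8% to 17% of a cohort for one subject, because the number entering with raised values is unknown. The liver part rests on the assumed Table 7 rows; the pancreatic part does not. The primary LDH analysis is unaffected. The change is worth making because it restores a commitment and costs little.

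**What to change.** - In SAP 3.8.3, add change from baseline by visit for ALP, ALT, AST, GGT, direct and indirect bilirubin, amylase and lipase, using the baseline definition in SAP 3.1.3.
- Present Tables 14.3.2.5 and 14.3.2.6 as baseline grade by worst post-baseline grade, by cohort and overall.
- State that the shift tables are read together with the change-from-baseline summaries, so that worsening within a grade is not lost.
- If the sponsor prefers not to restore the summaries, record the departure from protocol Section 13 in the SAP with its reason.

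Before the pancreatic shift table is built, one related inconsistency needs reconciling: Protocol 12.1.3.3 places Grade 3 above 2.5 x ULN, whereas SAP Table 8 starts it above 2.0 x ULN.

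The cost is a few lines of SAP text, added change summaries and two re-specified tables. Chemistry is already collected at Screening, Day 1 and every later visit, so no new data are needed.

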3.8.3.1 Hepatic Laboratory Tests: NCI CTCAE Grading

The liver functions test to be summarized via the National Cancer Institute (NCI) Common Terminology Criteria for Adverse Events (CTCAE) criteria are provided in Table 7.

Table 7: CTCAE Grading Criteria for Selected Liver Function Tests

	Grade/Criteria				
1	2	3	4		
> 1.0 - 3.0	>3.0 - 5.0	>5.0 - 20.0	> 20.0		
(x ULN)	(x ULN)	(x ULN)	(x ULN)		
>1.0 - 2.5	>2.5 - 5.0	>5.0 - 20.0	> 20.0		
(x ULN)	(x ULN)	(x ULN)	(x ULN)		
> 1.0 – 1.5	>1.5 – 3.0	>3.0 - 10.0	> 10.0		
(x ULN)	(x ULN)	(x ULN)	(x ULN)		
>1.0 - 2.5	>2.5 - 5.0	>5.0 - 20.0	>20.0		
(x ULN)	(x ULN)	(x ULN)	(x ULN)		
,	,	,	,		
	(x ULN) >1.0 - 2.5 (x ULN) > 1.0 - 1.5 (x ULN) >1.0 - 2.5 (x ULN)	(x ULN) (x ULN) >1.0 - 2.5 >2.5 - 5.0 (x ULN) (x ULN) > 1.0 - 1.5 >1.5 - 3.0 (x ULN) (x ULN) >1.0 - 2.5 >2.5 - 5.0 (x ULN) (x ULN)	(x ULN) (x ULN) (x ULN) >1.0 - 2.5 >2.5 - 5.0 >5.0 - 20.0 (x ULN) (x ULN) (x ULN) > 1.0 - 1.5 >1.5 - 3.0 >3.0 - 10.0 (x ULN) (x ULN) (x ULN) >1.0 - 2.5 >2.5 - 5.0 >5.0 - 20.0		

Grading criteria based on Common Terminology Criteria for Adverse Events (CTCAE) v4.03

Note: CTCAE ULN grades for direct bilirubin based on CTCAE ULN grades for total ("blood") bilirubin

3.8.3.2 Pancreatic Enzymes: NCI CTCAE Grading

Amylase and lipase values will be summarized via the NCI CTCAE criteria provided in Table 8.

Table 8: CTCAE Grading Criteria for Selected Pancreatic Enzyme Tests

Lab Test	Grade/Criteria					Grade/Criteria			
	1	2	3	4					
amylase	> 1.0 – 1.5	>1.5 – 2.0	>2.0 - 5.0	> 5.0					
	(x ULN)	(x ULN)	(x ULN)	(x ULN)					
limana	> 1.0 – 1.5	>1.5 – 2.0	>2.0 - 5.0	> 5.0					
lipase	(x ULN)	(x ULN)	(x ULN)	(x ULN)					
Grading criteria based on Common Terminology Criteria for Adverse Events (CTCAE) v4.03									

3.8.4 Anti-drug antibodies

The determination of anti-drug antibodies will not be included in the CSR.

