
Endpoints and Assessments
	
Safety and Tolerability Safety assessments will include evaluation of AEs and SAEs (including major adverse vascular event (MAVE criteria), clinical laboratory tests, ECGs, vital signs, and physical examinations. Safety evaluations will also include a determination of anti-drug antibodies (ADA).
 
Primary Efficacy:
 
 • The primary evaluation period is from Week 6 to Week 12. The primary efficacy endpoint is the change-from-baseline in serum LDH levels during this period, defined as the mean LDH values of Weeks 6, 8, 10, and 12 minus the baseline value of LDH. 
Secondary Efficacy:
 
 • Changes from baseline in LDH, total bilirubin, total hemoglobin, free hemoglobin, haptoglobin, reticulocytes, and hemoglobinuria, at each of the scheduled post-baseline assessment time-points. 
Pharmacokinetic:
 
 • Plasma concentrations of RA101495 and its major metabolites • Maximum plasma concentration (C_{max}) • Time corresponding to C_{max} (t_{max}) • Area under the drug concentration-time curves (AUC_{0-t}) • Plasma concentrations of eculizumab (Cohort B only) 
Pharmacodynamic:
 
 • Changes from baseline CH_{50} • Changes from baseline in sheep RBC (sRBC) lysis for classical complement pathway • Changes from baseline in Wieslab enzyme-linked immunosorbent assay

	
(ELISA) for alternative complement pathway
 
 • Changes from baseline in C5 levels 
Exploratory:
 
 • Changes from baseline in quality of life (QOL) questionnaires (e.g. EORTC QLQ-C30, FACIT-Fatigue, and EQ-5D) • Treatment satisfaction questionnaire • Mechanistic biomarkers (e.g. complement function, complement proteins, biomarkers of inflammation, biomarkers for thrombosis, biomarkers of liver function) • Pharmacogenomic analyses (optional)

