11.2.9 IMMUNOGENICITY

Blood samples for ADAs will be collected prior to dosing on Day 1 and on Day 29, Day 57, and Day 84 (or at the End-of-Study Visit) in all enrolled subjects. Samples will be sent to a central laboratory to determine the presence or absence of antibodies against RA101495 using a validated assay.

Detailed instructions regarding sample collection, processing, and shipping will be provided in a separate laboratory manual.

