2.2.3.10 Immunogenicity

Blood samples for ADAs will be collected prior to dosing on Day 1 and on Day 29, Day 57, and Day 84 (or at the End-of-Study Visit) in all enrolled subjects. Samples will be sent to a central laboratory to determine the presence or absence of antibodies against RA101495 using a validated assay.

Detailed instructions regarding sample collection, processing, and shipping will be provided in a separate laboratory manual.

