3.1.2 Reporting of Numerical Values

All clinical study data will be presented in patient data listings. Descriptive statistics (n, mean, standard error of the mean, standard deviation, median, minimum, and maximum) will be calculated by treatment group for continuous variables. Confidence intervals will be provided where appropriate. For continuous endpoints, the confidence interval for the mean will be based on the t-distribution (e.g., CLM in the SAS Proc Means procedure).

Frequencies and percentages will be presented by treatment group for categorical and ordinal variables. If there are missing values, the number of missing values will be presented, but without a percentage and the number of non-missing values used as the denominator.

Means, medians, standard deviations, standard error of the mean, and confidence intervals will be reported to one decimal place more than the data reported on the CRF or by the laboratory/vendor. Minimum and maximum will be reported to the same number of decimal places displayed on the CRF or by the laboratory/vendor. P-values will be reported to 4 decimal places.

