3.3 Analysis Endpoints

3.3.1 Safety Endpoints

Safety assessments will include evaluation of AEs and SAEs (including major adverse vascular event (MAVE criteria), surgery and other procedures, clinical laboratory tests, ECGs, vital signs, and physical examinations. Safety evaluation will also include a determination of anti-drug antibodies (ADA). Laboratory assessments will include PNH clone size.

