3.8 Safety Analysis

Safety analysis results will be presented using the Safety Population by cohort and overall.

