14.2.14.6	Summary of FACIT-Fatigue: Items Shift Table; Per Protocol
	Population
14.2.15.1	Summary of EQ-5D: Health State VAS Score; Safety
	Population
14.2.15.2	Summary of EQ-5D: Health State VAS Score; Per Protocol
	Population

Table Number	Table Title
14.2.15.3	Summary of EQ-5D: Individual Dimensions; Safety
	Population
14.2.15.4	Summary of EQ-5D: Individual Dimensions; Per Protocol
	Population
14.2.15.5	Summary of EQ-5D: Individual Dimensions Shift Table;
14.2.13.3	Safety Population
14.2.15.6	Summary of EQ-5D: Individual Dimensions Shift Table; Per
	Protocol Population
14.2.16.1	Summary of Treatment Satisfaction; Safety Population
14.2.16.2	Summary of Treatment Satisfaction; Per Protocol Population
14.3.1.1	Overall summary of Treatment Emergent Adverse Events;
14.3.1.1	Safety Population
14.3.1.2.1	Incidence of Treatment Emergent Adverse Events by System
14.3.1.2.1	Organ Class and Preferred Term; Safety Population
	Incidence of Treatment Emergent Adverse Events by System
14.3.1.2.2	Organ Class, Preferred Term, and Maximum Severity; Safety
	Population
	Incidence of Treatment Emergent Adverse Events by System
14.3.1.2.3	Organ Class, Preferred Term, and Relationship to Study Drug;
	Safety Population
	Incidence of Treatment Emergent Adverse Events Leading to
14.3.1.2.4	Discontinuation of Study Drug by System Organ Class and
	Preferred Term; Safety Population
14.3.1.3	Listing of Serious Adverse Events by System Organ Class and
11.3.1.3	Preferred Term; Safety Population
	Incidence of Thrombotic Treatment Emergent Adverse Events
14.3.1.4	by System Organ Class, and Preferred Term; Safety
	Population
14.3.1.5	Summary of Injection Site Reaction Assessments; Safety
	Population
14.3.2.1	Summary of Hematology Values; Safety Population
14.3.2.2	Summary of Clinical Chemistry Values; Safety Population
14.3.2.3	Summary of Coagulation Values; Safety Population
14.3.2.4	Summary of C-Reactive Protein and Creatine Phosphokinase
1	Values; Safety Population
14.3.2.5	Summary of Liver Function Test Values – NCI CTCAE
11.5.2.5	Grading; Safety Population
14.3.2.6	Summary of Pancreatic Enzyme Test Values – NCI CTCAE
	Grading; Safety Population
14.3.2.7	Summary of Urinalysis Values; Safety Population
14.3.3	Summary of PNH Clone Size Values
	Safety Population

Table Number	Table Title
14.3.4	Summary of Vital Signs; Safety Population
14.3.5.1	Summary of ECG Interpretation; Safety Population
14.3.5.2	Summary of ECG Values; Safety Population

Figure Number	Figure Title

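### SAP 3.8.4 keeps anti-drug antibodies out of the CSR, leaving one declared safety evaluation of eight with no planned table or listing

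*SAP*

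**What the plan says.** SAP 3.8.4 is a single sentence: "The determination of anti-drug antibodies will not be included in the CSR". It gives no reason and names no other report.

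Elsewhere the SAP treats ADA as part of the study's safety data:

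- SAP 3.3.1, the safety part of the Analysis Endpoints section: "Safety evaluation will also include a determination of anti-drug antibodies (ADA". Protocol sections 2 (synopsis), 7.2.1 and 8.1 say the same.
- SAP 3.1.2, with no exception stated: "All clinical study data will be presented in patient data listings".
- SAP 2.2.3.10: "Blood samples for ADAs will be collected prior to dosing on Day 1 and on Day 29, Day 57, and Day 84", in all enrolled subjects. An early End-of-Study Visit also includes an ADA sample (Protocol 8.4.1).
- Protocol 11.2.9: "Samples will be sent to a central laboratory to determine the presence or absence of antibodies against RA101495 using a validated assay".

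SAP section 5, which lists the planned tables, figures and listings, has no ADA or immunogenicity entry.

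**The concern.** The SAP keeps ADA as a safety evaluation and keeps its sampling, but removes its result from the report that the SAP exists to specify. Safety and tolerability is the first objective listed in both documents, and the product is a peptide injected daily for 12 weeks. If the plan is followed as written, a reader of the CSR cannot see how many subjects became antibody-positive, or when. SAP section 1 requires analyses not specified in the SAP to be identified as post hoc or exploratory, so an ADA summary added later would carry that label.

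**Working it through.** No power, alpha or sample-size figure is involved. The check matches the safety items named in SAP 3.3.1 to the outputs in SAP section 5.

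| Safety item in SAP 3.3.1 | Planned output in SAP section 5 |
|---|---|
| AEs and SAEs, including MAVE | Tables 14.3.1.1 to 14.3.1.4; Listings 16.2.10.1 to 16.2.10.5 |
| Surgery and other procedures | Listing 16.2.14 |
| Clinical laboratory tests | Tables 14.3.2.1 to 14.3.2.7; Listings 16.2.12.1 to 16.2.12.4 |
| ECGs | Tables 14.3.5.1 and 14.3.5.2; Listing 16.2.15 |
| Vital signs | Table 14.3.4; Listing 16.2.13 |
| Physical examinations | Listing 16.2.16 |
| PNH clone size | Table 14.3.3, "Summary of PNH Clone Size Values"; also in the hematology listing (SAP 3.8.3) |
| ADA | None |

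Result: 7 of 8 items have output, and ADA is the exception.

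**Does the way of counting matter?** Counting AEs and SAEs separately gives nine items. Treating PNH clone size as a laboratory test gives seven. ADA is the only item without output either way. The longer list of safety assessments in SAP 2.2.3, counted as ten items, gives the same answer for immunogenicity: Neisseria testing has Listing 16.2.2.7, pregnancy testing has 16.2.2.8 and urinalysis has 16.2.12.4.

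**Samples affected.** Planned enrolment is 8 to 12 in Cohort A and 6 to 8 in Cohort B.

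- Subjects: 8 + 6 = 14 to 12 + 8 = 20.
- Scheduled ADA samples, four per subject: 4 × 14 = 56 to 4 × 20 = 80.
- Post-dose samples (Days 29, 57 and 84): 3 × 14 = 42 to 3 × 20 = 60.

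These counts assume that every subject attends all four visits and that no one is replaced.

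**How the documents treat comparable cases.** SAP 3.9.3 says that CH50 will not be analyzed, and CH50 is also absent from the SAP's assessment and endpoint lists (2.2.6 and 3.3.4). ADA was dropped from reporting but stays in 3.3.1. Where the protocol foresees reporting outside the main study report, it says so, for biomarkers (11.6.3) and for pharmacogenomics (11.6.4). Its immunogenicity section (11.2.9) has no such wording.

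**The case against.** The strongest reply is that 3.8.4 is a deliberate, openly stated exception. A specific rule normally governs a general one such as 3.1.2, and section 5 is consistent with 3.8.4, so a programmer would know what to produce. Protocol 13.3.4 plans no ADA summary, so no protocol-specified analysis is lost. This stands, and it limits the point: the production instructions are clear and no pre-specified test has been deleted. It does not explain why 3.3.1 still declares the evaluation, why 3.1.2 admits no exception, or where the results will appear.

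Three stronger readings are tempting, but the documents do not support them:

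- A reader might infer that samples will go untested or results will never be reported. SAP 3.8.4 cancels neither sampling nor assay; it speaks only of the CSR.
- A reader might see a further conflict with SAP 3.8: "Safety analysis results will be presented using the Safety Population by cohort and overall". That sentence sets the population and grouping for safety results that are presented. It does not promise that every safety item will be presented.
- A reader might infer that a planned analysis relating ADA to LDH or drug concentration is lost. Neither document plans one, and LDH and RA101495 concentrations remain visible in Listings 16.2.6 and 16.2.8.1.

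A smaller repair is also arguable: state the reason and the place of reporting in 3.8.4, and write the exception into 3.1.2. That would reconcile the text but would still leave the CSR without the result.

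**Conclusion.** The point holds as a mismatch between a declared safety evaluation and the planned outputs. ADA is the only one of the eight safety items in SAP 3.3.1 with no table or listing, and no reason or alternative report is given. Four scheduled samples per subject are affected, 56 to 80 in total under the enrolment and attendance assumptions stated above. The statement that ADA is the only such item applies to the items in 3.3.1, not to all study data: the protocol-deviation listing promised in SAP 3.4.2 also has no entry in section 5. The primary efficacy endpoint and its test are unaffected. The correction should be made, because it is cheap and concerns the first-listed objective.

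**What to change.** Replace the sentence in SAP 3.8.4 with a plan that has these elements:

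- A listing of all ADA results by subject and visit.
- A summary of the number and percentage of ADA-positive subjects by visit (Days 1, 29, 57, and 84 or End-of-Study Visit), by cohort and overall, in the Safety Population. The denominator is subjects with a non-missing ADA result at that visit.
- Identification of subjects already positive at the Day 1 pre-dose sample.
- If assay results are not available when the CSR is finalized, a statement to that effect in the CSR, with both outputs issued as a CSR addendum.

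Add the table and the listing to SAP section 5. Showing LDH and RA101495 concentration beside ADA in the listing is optional. Both are scheduled at the same four visits (SAP Table 2).

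The cost is one paragraph of SAP text and two outputs, with no new sampling. The documents do not show when assay results will be ready, so an addendum may be needed.
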